- Withdrawal of Approval: If an IRB withdraws the approval to conduct this study for any reason, the investigator will notify the Sponsor as soon as possible, but in no event later than five working days after the withdrawal of the approval
- Progress Reports: The investigator will submit progress reports on the investigation to the Sponsor and the reviewing IRB at regular intervals, but in no event less often than yearly.
- Deviations from the Investigational Plan: The investigator must notify the Sponsor and the reviewing IRB of any deviation from the Investigational Plan to protect the life or physical well-being of a subject in an emergency. This notice must occur as soon as possible, but in no case longer than five working days following the occurrence of the deviation.
- Informed Consent: If the investigator uses a device without obtaining informed consent, the investigator shall report the use to the Sponsor and the IRB within 5 working days after the use occurs.
- Final Report: Within three months after the termination or completion of the study or the investigator's part in the study, the investigator shall submit a final report to the Sponsor and the IRB.
- Other Reports: Upon request from the IRB or the FDA, the investigator shall provide accurate, complete and current information about any aspect of the study.

Each investigator is responsible for ensuring that the study is conducted according to this protocol and that signed Informed Consent is obtained from each subject prior to their inclusion in this study.

11. Adverse Events and Serious Adverse Events

General

All observed or volunteered adverse events regardless of treatment group or suspected causal relationship to the investigational product(s) will be reported as described in the following sections.

For all adverse events, the investigator must pursue and obtain information adequate both to determine the outcome of the adverse event and to assess whether it meets the criteria for classification as a serious adverse event requiring immediate notification to the Hologenix contact. For all adverse events, sufficient information should be obtained by the investigator to determine the causality of the adverse event. The investigator is required to assess causality. For adverse events with a causal relationship to the device, follow-up by the investigator is

required until the event or its sequelae resolve or stabilize at a level acceptable to the investigator, and the Hologenix contact concurs with that assessment.

Adverse Event Reporting

For serious adverse events, the reporting period to Hologenix or its designated representative begins from the time that the subject provides informed consent, which is obtained prior to the subject's participation in the study, i.e., prior to undergoing any study-related procedure and/or receiving investigational product, through and including 28 calendar days after the last administration of the investigational product. Any serious adverse event occurring any time after the reporting period must be promptly reported if a causal relationship to investigational product is suspected. Adverse events (serious and non-serious) should be recorded on the CRF from the time the subject has undergone one treatment through last subject visit.

Definition of an Adverse Event (AE)

An adverse event is any untoward medical occurrence in a clinical investigation subject administered a product or medical device; the event need not necessarily have a causal relationship with the treatment or usage. Examples of adverse events include but are not limited to:

- Abnormal test findings;
- Clinically significant symptoms and signs or diagnosis;
- Changes in physical examination findings;
- Hypersensitivity;
- Progression/worsening of wound.

Protocol Specific AE Definition/Collection

For the purposes of this study, only AEs that are directly related to the study product, diabetes (including labs & kidney function) or wound healing (including infections related to the wound) will be collected and reported as these events may affect outcomes and analysis of data. AEs not related to the aforementioned product or diagnoses are not relevant to the subject outcomes of this research or data analysis (such as nausea, emesis, pain, constipation, diarrhea, mood disorders, respiratory diagnoses, cardiac related events, etc). AEs that do not fall under this protocol specific definition will be assessed and treated as per standard of care. SAEs will be collected as per the usual SAE guidelines (see section on reporting SAEs). In addition, planned procedures related to the study wound for a subject during the same hospitalization (as these subjects will be recruited while in the hospital because they have an infection in their foot wound/ulcer) for incision/debridement/amputation will be considered part of their continuation of SOC and not adverse events unless a complication, new infection or new wound occurs.

Definition of Serious Adverse Event (SAE)

A Serious Adverse Event (SAE) is any AE that has any serious unfavorable and unintended sign, symptom, or disease temporally associated with the use of the devices, whether or not considered related, including those that:

- · results in death
- is life-threatening
- requires inpatient hospitalization or causes prolongation of existing hospitalization
- results in persistent or significant disability/incapacity
- is a congenital anomaly/birth defect
- requires intervention to prevent permanent impairment or damage

Medical and scientific judgment should be exercised in determining whether an event is an important medical event. An important medical event may not be immediately life-threatening and/or result in death or hospitalization. However, the important medical event should be reported as serious, if it is determined that the event may jeopardize the subject and/or may require intervention to prevent one of the other adverse event outcomes.

Causality Assessment of Adverse Events

The investigator's assessment of causality must be provided for all adverse events (serious and non-serious); the investigator must record the causal relationship in the CRF, as appropriate, and report such an assessment in accordance with the serious adverse reporting requirements if applicable. An investigator's causality assessment is the determination of whether there exists a reasonable possibility that the cleared medical device caused or contributed to an adverse event. If the investigator does not know whether or not medical device caused the event, then the event will be handled as "related to medical device" for reporting purposes. (see Section on Reporting Requirements). If the investigator's causality assessment is "unknown but not related to investigational product", this should be clearly documented on study records.

In addition, if the investigator determines a serious adverse event is associated with study procedures, the investigator must record this causal relationship in the source documents and CRF, as appropriate, and report such an assessment in accordance with the serious adverse event reporting requirements, if applicable.

Adverse Event Severity Assessment

The Investigator will provide an assessment of the severity of each adverse reaction by recording a severity rating on the appropriate SAE reporting page of the subject's file. Severity, which is a description of the intensity of manifestation of the SAE, is distinct from seriousness, which implies a patient outcome or SAE-required treatment measure associated with a threat to life or functionality. Severity will be assessed according to the following scale.

If required on the adverse event case report forms, the investigator will use the adjectives MILD, MODERATE, or SEVERE to describe the maximum intensity of the adverse event. For purposes of consistency, these intensity grades are defined as follows:

MILD	Does not interfere with subject's usual function.
MODERATE	Interferes to some extent with subject's usual function.
SEVERE	Interferes significantly with subject's usual function.

Note the distinction between the severity and the seriousness of an adverse event. A severe event is not necessarily a serious event. For example, a headache may be severe (interferes significantly with subject's usual function) but would not be classified as serious unless it met one of the criteria for serious adverse events, listed above.

Withdrawal Due to Adverse Events (See Also Section on Subject Withdrawal)

Withdrawal due to adverse event should be distinguished from withdrawal due to insufficient response, according to the definition of adverse event noted earlier, and recorded on the appropriate adverse event CRF page.

When a subject withdraws due to a serious adverse event, the serious adverse event must be reported in accordance with the reporting requirements defined below.

Eliciting Adverse Event Information

The investigator is to report all directly observed adverse events and all adverse events spontaneously reported by the study subject. In addition, each study subject will be questioned about adverse events by a member of the research staff.

Reporting Requirements

Each adverse event is to be assessed to determine if it meets the criteria for serious adverse events. If a serious adverse event occurs, expedited reporting will follow local and international regulations, as appropriate.

Serious Adverse Event Reporting Requirements

If a serious adverse event occurs, Hologenix is to be notified within 24 hours of awareness of the event by the investigator. In particular, if the serious adverse event is fatal or life-threatening, notification to Hologenix must be made immediately, irrespective of the extent of available adverse event information. This timeframe also applies to additional new information (follow-up) on previously forwarded serious adverse event reports as well as to the initial and follow-up reporting of Exposure during pregnancy cases.

In the rare event that the investigator or member of the research team does not become aware of the occurrence of a serious adverse event immediately (e.g., if an outpatient study subject

initially seeks treatment elsewhere), the investigator or member of the research team is to report the event within 24 hours after learning of it and document the time of his/her first awareness of the adverse event.

For all serious adverse events, the investigator is obligated to pursue and provide information to Hologenix in accordance with the timeframes for reporting specified above. In addition, an investigator may be requested by Hologenix to obtain specific additional follow-up information in an expedited fashion. This information may be more detailed than that captured on the adverse event case report form. In general, this will include a description of the adverse event in sufficient detail to allow for a complete medical assessment of the case and independent determination of possible causality. Information on other possible causes of the event, such as concomitant medications and illnesses must be provided. In the case of a subject death, a summary of available autopsy findings and/or a copy of the death certificate must be submitted as soon as possible to Hologenix or its designated representative.

All AEs/SAEs should be followed until resolution.

Non-Serious Adverse Event Reporting Requirements

All adverse events will be reported on the adverse event page(s) of the CRF. It should be noted that the form for collection of serious adverse event information is not the same as the adverse event CRF. Where the same data are collected, the forms must be completed in a consistent manner. For example, the same adverse event term should be used on both forms. Adverse events should be reported using concise medical terminology on the CRFs as well as on the form for collection of serious adverse event information.

Reporting Requirements to Regulatory Authorities

Adverse events reporting, including suspected serious unexpected adverse reactions, will be carried out in accordance with applicable local regulations.

12. Committees

Data and Safety Monitoring Board

The study will be under the oversight of an independent DSMB that will assess the accumulated safety data on an ongoing basis. The role and responsibilities of the DSMB will be predefined in the DSMB charter.

13. Publication Policy

The preparation and submittal for publication of manuscripts containing the study results shall be in accordance with a process determined by mutual written agreement among the investigator and the Hologenix contact. The publication or presentation of any study results shall comply with all applicable privacy laws, including, but not limited to, the Health Insurance Portability and Accountability Act of 1996.

PI: [name]

14. Bibliography

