The Celliant[®] Diabetic Medical Sock is an investigational device and is not approved in the United States to provide infrared radiation (IR) to increase tissue oxygenation or to promote complete wound closure by increasing blood flow and circulation or to reduce pain in diabetic patients with foot ulcers.

However, the US FDA has determined the Celliant Products to be medical devices as defined in section 201(h) of the Act and are also general wellness products. The Celliant Products are medical devices because they are intended to affect the structure or function of the body of man by temporarily promoting increased local blood flow at the site of application in healthy individuals.

Proposed Indications for Use

The Celliant® Diabetic Medical Sock is intended to provide infrared radiation (IR) to increase tissue oxygenation (via oxygen saturation, S_tO_2) as measured by hyperspectral imaging (HSI) resulting in increased blood flow and local circulation in the affected area which may influence wound closure. In a clinical study, adult subjects (22 years and older) with diabetic foot ulcers showed an increase in tissue oxygenation and blood flow and local circulation with positive wound closure outcomes compared to subjects wearing non-Celliant® Diabetic Medical Socks. The Celliant® Diabetic Medical Sock may also reduce/improve pain

Benefits and Risks

Potential Benefits to the Subjects

There is no promise or guarantee that this product will help heal the subject's wound, but the potential benefit of wearing Celliant® Diabetic Medical Socks is that adults with diabetic foot ulcers may experience improved tissue oxygenation and improved wound closure outcomes and possible pain reduction compared to adults not wearing Celliant Socks. The clinical results may prove this hypothesis. Moreover, the potential benefits may extend beyond the immediate closure of chronic foot ulcers. The effects of IR on the tissue of the feet will tend to prevent any further lesions or ulcers developing. By increasing the tissue oxygenation, reducing inflammation, and stimulating collagen formation in the dermis, the skin may be "strengthened" and small traumas which would previously have progressed into a chronic wound may be healed up without even being noticed.

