- Major immunodeficiency including HIV.
- Is pregnant or plans to become pregnant
- Is nursing or actively lactating

Celliant Clinical Trial Protocol
PI: [name]
Protocol #: HGX2020-01

 Developmental disability/significant psychological disorder that in the opinion of the investigator could impair the subject's ability to provide informed consent, participate in the study protocol or record study measures, including untreated schizophrenia, bipolar disorder and psychiatric hospitalization within the last 2 years.

 Active alcohol or substance abuse in the opinion of the investigator that could impair the subject's ability to provide informed consent, participate in the study protocol or record study materials

Withdrawal of Subjects

Subjects may withdraw from the study at any time at their own request, or they may be withdrawn at any time at the discretion of the PI for safety, behavioral, or administrative reasons. If a subject does not return for a scheduled visit, every effort should be made to contact the subject, per institutional protocol. In any circumstance, every effort should be made to document subject outcome. The Investigator should inquire about the reason for withdrawal, request that the subject return for a final visit, if applicable, and follow up with the subject regarding any unresolved AE's.

Any related SAE occurring within 14 days following subject discontinuation must be reported to Hologenix and be followed up until stabilization or resolution. If the Subject withdraws from the study, and also withdraws consent for disclosure of future information, no further study evaluations will be performed, and no additional data will be collected. The PI may retain and continue to use any data collected before such withdrawal of consent.

The Investigator may choose to withdraw their own participation or discontinue a Subject from study with or without their consent for any of the following:

- Adverse Events
- Non-compliance
- Safety
- Complications
- Unforeseen events

A patient who experiences the noted changes, relative to previous measures, in the following parameters will be terminated early from study participation

- An increase in ulcer size by 50% or more prior to debridement from previous visit.
- An increase in pain rating by 50% or more from previous visit.
- Presence of infection as determined by 2 more bacterial infection indicators that requires treatment outside the study scope

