- Presence of osteomyelitis that requires treatment outside the study scope.
- Need for wound management outside the study scope

Celliant Clinical Trial Protocol
PI: [name]
Protocol #: HGX2020-01

 Or for any reason that may, in the opinion of the Investigator, affect negatively the wellbeing of the subject.

If for any reason the subject is withdrawn from the clinical investigation, the Investigator will inform the subject accordingly.

3. Clinical Investigation Plan

Description of Trial Design

This study is designed as a prospective, multi-center, double-blind, 1:1 randomized clinical trial to assess the clinical safety and efficacy of Celliant® Diabetic Medical Socks to increase tissue oxygenation and complete wound closure.

Investigational Sites

University of Texas Southwestern, Department of Plastic Surgery

PI: [name], DPM, MPH

Location: Dallas, TX

Parkland Hospital, Department of Plastic Surgery

PI: [name], DPM Location: Dallas, TX

Duration of Subject Participation

- Screening: Within 7 days Run-In initiation
- Run in Evaluation: 2 weeks of evaluation
- Treatment period: Up to 12 weeks
- Follow-up period: Up to 3 months post wound closure event
- Total duration of subject participation: Up to 28 weeks

Screening and Enrollment

Patients who present to the investigator's institution (through clinic admission, direct transfer from another facility, or through the emergency room) may be recruited to participate in the study. No direct marketing for subject recruitment will be done.

Patients approached for study participation will be at least 22 years of age at the time of consent, will undergo wound assessment, and meet all eligibility requirements. Those meeting eligibility criteria for the study will have the study explained to them by the Investigator. An Informed Consent Form will be provided to sign according to Section 11 prior to undergoing any study procedures. Patients will be encouraged to ask questions of the investigators. It will be made clear to the patient that not participating in the study will in no way influence the treatment plan or the relationship with the physician.

Celliant Clinical Trial Protocol
Protocol #: HGX2020-01

Wound Selection

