- 8. Perform SPP and tcPO2 measurements at Visit 4 (maybe be taken instead at visit 5 or 6 if subject has not been wearing their treatment sock leading up to the visit or misses this visit).
- 9. Collect all relevant concomitant medication
- 10. Perform pain assessment.
- 11. Redress the wound with standard of care (if wound is still active) and apply Celliant Active or Control Sock and apply offloading (if indicated).
- 12. Wound will be offloaded.
- 13. Provide subject with any additional medical socks needed until the next visit. Instruct the subject to change the socks if they become wet, soiled, or bloody and under any conditions dictated by PI instructions. Instruct the subject that they must wear the sock at all times and that including the 3 hours leading up to the next study visit.

Study Visit - Wound Closed

- 1. The study wound is defined as closed when there is complete skin re-epithelialization without drainage or dressing requirements confirmed by the evaluating physician at 2 consecutive study visits 2 weeks apart.
- 2. At this visit the subject will perform the EOS evaluation and enter the follow-up phase of the study.

Study Visit 12/EOS

- 1. If the study wound closes prior to the 12-week study mark, subjects will perform EOS visit at the time of wound closure. See Study Visit Wound Closed.
- 2. A subject whose wound does not close completely by week 12 will exited from the study after the week 12 wound evaluation.
- 3. Document study compliance information from the subject
 - a. Amount of time the sock was worn throughout the week
 - b. Was it worn during the day/night?
 - c. When/why the sock was changed.

- d. Has the sock been on in the 3 hours leading up to the appointment?
- 4. Remove sock and dressing and immediately perform hyperspectral imaging of the dorsal and plantar aspects of the foot if wound is active or closed.
- 5. Assess target ulcer (if wound has closed, document as such, perform steps 7-12 and skip to Study Visit Wound Closed).
- 6. If the subject still has a large enough wound, collect 4 tissue samples. Two in RNA later and two in DNA/RNA shield.
- 7. Perform standardized photography of the study wound.
- 8. Assess the ulcer area (cm²), perimeter (cm), and greatest depth (cm) using the inSight device.
- 9. Perform SPP if wound is active or closed.
- 10. Perform tcpO2 if wound is active or closed.
- 11. Perform pain assessment
- 12. Ask the subject if they thought they were in the active or control group

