The VAS is the most commonly used scale for assessing pain [60]. The VAS is a simple scale that consists of a 10cm line anchored at one end by a label that indicates total absence of the measure being evaluated and at the other end by a label that indicates the worse imaginable presence of the measure being evaluated. The subject marks on the line the spot for the intensity of the measure, which is then measured using a ruler (in mm units).

Infection Evaluation

The following clinical indicators of significant bacterial infection will be recorded as present or absent for the study wound. 'Significant Bacterial Infection Clinical Indicators' are defined in this study as those presenting as excessive beyond which would typically be expected given the clinical condition and nature of the wound type.

- local heat
- spreading redness
- swelling
- increased purulent exudate (draining pus)
- odor
- cellulitis
- loss of function
- fevers
- chills

Sock Use Instructions

The subjects will be provided with 10 pairs of socks on the initial visit and instructed that the socks may be washed as normal laundry as needed (bleach or no bleach). Subjects will be supplied additional pairs as needed on a case by case basis. The sock change frequency will be dictated by the physician; however, the subject will be instructed to change the sock as with any other sock if it becomes wet, soiled, or bloody.

Patient Reported Outcomes

The Diabetic Foot Ulcer Scale – Short Form (DFS-SF) (Appendix B) will be used to collect patient reported outcomes in this trial. The DFS questionnaire is designed to assess the impact of foot ulcers and their treatment on quality of life in people with diabetes.

Excluded Medications/Treatments

During the study procedures, the study subjects will refrain from using hyperbaric oxygen therapy (HBOT) and any cellular or tissue-based products (RegranX etc).

Standard of Care

- All study wounds will be debrided per physician discretion and documented.
- Wound Dressing: Two wound care treatments will be available, depending on wound status and physician discretion

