Internal audits are done periodically to assure regulations, guidelines and protocols are adhered to appropriately. Patient binders are reviewed for proper informed consent process documentation, case report forms are compared to the source documents and reviewed for accuracy and an independent review of the inclusion and exclusion criteria using a checklist. Additionally, the use of an auditing and monitoring tool which includes sections on consent, HIPAA, on study/treatment, off treatment/off study and a general section. Weekly meetings occur to go over each study. If there are any issues that arise, they are brought up and discussed at the meeting.

4. Statistical Analyses

General Statistical Considerations

This study is a prospective, sham-controlled, subject and evaluator blinded, 1:1 randomized, multicenter clinical study. The duration of the study is up to four months for randomized subjects. Sample size may not be reduced less than the expected total enrollment of 254 evaluable subjects total but may increase up to a total of 2500 evaluable subjects. Sample size will increase based on actual attrition that is expected to be between 5 and 15%.

The purpose of this study is to evaluate safety and efficacy outcomes related to the Celliant Sock (CS). The p-value thresholds for determining statistical significance are 0.05 and 0.025 for 2- and 1-sided tests, respectively, unless otherwise specified.

Protocol #: HGX2020-01

Data will be presented using summary statistics. For example, continuous data may be displayed with the mean, median, minimum, maximum, and/or standard deviation, while categorical data may be displayed as proportions and counts.

Any changes to the analysis of the trial data will be documented either in a future protocol amendment or in the SAP.

Randomization

Randomization will be conducted in a 1:1 ratio of the Treatment Group (Celliant Sock, n=127) or to a sham Control Group (placebo sock, n=127). Randomization will be performed within randomly selected block sizes of 3 and 6 with equal probability of group assignment stratified by study center and wound size (greater than size of 4 cm²).

A Sponsor-designated independent statistical consultant will provide the randomization list. Sponsor personnel directly involved in the management, conduct, and reporting of the study will not have access to randomization assignments until the study is completed.

Analysis Population

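### The mandatory 50% pain rule is purely relative and ends study participation, not only sock use, so randomised subjects can leave before the week-12 assessments on trivial VAS changes

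*Combined protocol and SAP*

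**What the plan says.** Section 2, Withdrawal of Subjects, first lists reasons for which an investigator may discontinue a subject. It then gives a second, compulsory list: "A patient who experiences the noted changes, relative to previous measures, in the following parameters will be terminated early from study participation". One entry is "An increase in pain rating by 50% or more from previous visit". The list ends with a discretionary clause for anything that may "affect negatively the wellbeing of the subject".

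Section 3, Degree of Pain Rating, uses a 100 mm line on which 0 (no pain) is a valid score, "which is then measured using a ruler (in mm units". The Schedule of Events has pain assessed at week 0, weeks 1-11 and the end-of-study visit. The eligibility criteria set no pain threshold.

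For subjects who leave, Section 2 says "In any circumstance, every effort should be made to document subject outcome" and asks for a final visit where applicable. It stops further evaluations outright only for subjects who also withdraw consent to disclosure of future information.

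In Section 4, the primary contrast and complete closure are both assessed at 12 weeks in all randomised subjects, and VAS pain is third in the testing hierarchy. The Proposed Indications for Use say that the sock "may also reduce/improve pain". On attrition, the plan says "Sample size will increase based on actual attrition that is expected to be between 5 and 15" percent.

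**The concern.** Two features combine. First, the threshold is relative only, so the worsening that forces exit shrinks with the previous score. A subject with little pain can be removed for a millimetre or two, while a subject with severe pain can worsen to the top of the scale and stay in. Exit depends on pain level as much as on deterioration.

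Second, the consequence is the end of study participation. Ending sock use would be a treatment decision, and follow-up could go on. Ending participation leaves no scheduled week-12 measurement of oxygenation, closure or pain in a trial whose main contrasts are at week 12 in everyone randomised. The event that removes the subject is itself a rise in a ranked endpoint.

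**Working it through.** **What follows from the text alone.** Exit needs current score ≥ 1.5 × previous score, with a maximum of 100 mm.

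| Previous score (mm) | Rise that forces exit (mm) |
|---|---|
| 2 | 1 |
| 10 | 5 |
| 20 | 10 |
| 40 | 20 |
| 60 | 30 |
| 66 | 33 (to 99) |
| 67 or more | impossible, since 1.5 × 67 = 100.5 |
| 0 | undefined (division by zero) |

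The same 20 mm worsening forces exit from 40 mm (20/40 = 50%) but not from 41 mm (20/41 = 48.8%). Going from 67 to 100 mm is 33/67 = 49%, so the subject stays in. Thirteen scheduled readings give 12 comparisons after randomisation.

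**How often it could fire by chance.** The plan gives no figure to reproduce. It states neither a VAS distribution nor a visit-to-visit error SD, so every input here is an assumption. Each setting simulates 200,000 subjects with constant true pain (normal, clipped to 0-100), adds normal error, rounds to 1 mm, and flags any visit at least 1.5 times a non-zero previous one. Rises from 0 are not counted. There is no early closure in the table.

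| True pain, mean (SD), mm | Error SD 3/5/8/10 mm, independent weekly error | Same, AR(1) correlation 0.7 |
|---|---|---|
| 30 (20) | 26/48/73/84% | 15/25/43/55% |
| 45 (25) | 13/28/53/66% | 7/13/25/34% |
| 60 (20) | 2/9/32/49% | 1/2/8/14% |

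The table was checked with a separate run and agreed within about one percentage point.

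**Variations, independent error**
- Closing early shortens the series: "If the study wound closes prior to the 12-week study mark, subjects will perform EOS visit at the time of wound closure". If 25% close at a random week (the plan's assumed closure rate under Celliant), the first row becomes 23/43/67/76%.
- If, in addition, 70% of subjects always score 0, multiply by 0.3: 7/13/20/23%. If 80% do, multiply by 0.2: 5/9/13/15%.
- If error is proportional to the score (CV 5/10/12/15%, 30 mm mix, 25% closing): 0.4/4/12/30%.
- A trigger at week 12 itself loses no week-12 data. Counting only visits 1-11 lowers the rates by at most about 2 points (for example 48% to 46%).

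**Who is removed.** At error SD 5 with independent error, mean true pain of exited versus kept subjects is 18 vs 42, 20 vs 55 and 29 vs 63 mm in the three mixes.

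**Effect of a minimum rise.** Requiring a rise of at least 20 mm as well as 50% cuts chance exits to 0% at SD 3 and about 1-2% at SD 5, but leaves 22-51% at SD 8-10 with independent error.

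**The case against.** The strongest reply is that the size rests wholly on assumed inputs. Weekly scores in chronic pain are probably correlated, which lowers the rates a good deal, and several plausible cases fall below or inside the 5-15% attrition already expected. This stands: the upper figures should carry little weight, and the defect should be judged on the wording of the rule.

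The analysis also has safeguards. All randomised subjects are analysed. The MMRM uses visits before exit, and imaging and wound assessment come before the pain score at each visit, so the triggering visit is recorded. Imputation applies above 7.5% missing for the first two endpoints. Enrolment rises with actual attrition, so the evaluable count is not the main harm. All true, but each of these models or replaces the week-12 outcomes of those removed; none observes them.

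The rule is also a safety measure, since pain or discomfort is a listed device risk. That argues for stopping the sock, and the fix keeps this.

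Three stronger readings are tempting:
- *All data collection stops at exit.* The text asks for best efforts and a final visit where applicable. What it lacks is a scheduled week-12 assessment.
- *The rule favours one arm.* More true worsening under Control would send more Control subjects out. A sock that lowers scores could send more Celliant subjects out, because low scores trigger more easily. The documents do not settle the direction.
- *The oxygenation or closure result is biased by a known amount.* No such bias has been calculated, and the documents give no link between pain exits and those outcomes.

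**Conclusion.** The concern holds in a limited form. The text alone establishes that the rule is compulsory, has no minimum rise, is undefined at 0, cannot apply from 67 mm upward, and ends participation with no week-12 assessment scheduled. That makes follow-up depend on a ranked endpoint and on pain level.

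The frequency is not established. Under stable true pain, mean 30-60 mm and error SD 3-10 mm, chance exits run from about 2% to 84% with independent error and from about 1% to 55% with correlation 0.7. They fall below 1% if error is small and proportional. They may therefore fall below, within or above the expected attrition. Under these models exits concentrate in subjects with low pain. The rule should be changed because the remedy is cheap and keeps the protection, not because a particular bias has been shown.

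**What to change.** In Section 2, Withdrawal of Subjects:
1. Let the pain trigger stop the sock and prompt physician review, but not by itself end study participation. Keep the wellbeing clause.
2. Continue hyperspectral imaging, closure assessment and VAS at the already scheduled visits through week 12, analysed as randomised.
3. Say what happens when the previous score is 0.
4. Add an absolute minimum rise, chosen by the sponsor, to the 50% condition. A floor does not replace items 1 and 2: 20 mm alone still leaves about 22-51% chance exits at error SD 8-10 mm with independent error.

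The cost is protocol wording plus the remaining visits. At the 35 dollars per visit in Subject Compensation, a subject who triggers at visit 1 has 11 visits left, so stipends are at most 11 × 35 = 385 dollars, with staff and imaging time on top. Some off-sock data will enter the intention-to-treat analysis, which is consistent with a population defined regardless of wear.
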